The COVID-19 global pandemic may present challenges to the normal conduct of this study (including AE and laboratory assessments), requiring the implementation of potential mitigation strategies described in [Appendix B](#).

Figure 1: Study Design Schema

[figure not shown]

Table 3: Schedule of Activities

Visit Day (Range)	Screening	Days -28 to -1	DBVC Period						OLE Period					Safety Follow-Up
		Baseline/ Day 1 (± 3 d)	Wk 2 ^a (± 3 d)	Wk 4 ^a (± 3 d)	Wk 8 ^a (± 3 d)	Wk 12 ^a (± 3 d)	Wk 16/ EOT1 ^b (± 3 d)	Wk 18 ^a (± 3 d)	Wk 20 ^a (± 3 d)	Wk 24 ^a (± 3 d)	Wk 28 ^a (± 3 d)	Wk 32 EOT2/ET ^c (± 3 d)	Unscheduled Visit	
Administrative procedures														
Informed consent		X												
Inclusion/exclusion criteria review	X	X												
Demography and medical history	X													
Prior/concomitant medications	X	X	X	X	X	X	X	X	X	X	X	X	X	
Contact IRT	X	X	X	X	X	X	X	X	X	X	X			
Distribute reminder cards	X	X	X	X	X	X	X	X	X	X	X			
Distribute eDiary	X													
Apply study drug in clinic		X	X	X	X	X	X	X	X	X	X			
Weigh/dispense study drug		X	X	X	X	X	X	X	X	X	X			
Collect/weigh study drug			X	X	X	X	X	X	X	X	X	X		
Assess study drug compliance			X	X	X	X	X	X	X	X	X			
Safety assessments														
AE assessments	X	X	X	X	X	X	X	X	X	X	X	X	X	
Comprehensive physical examination ^d	X											X		
Height and body weight	X											X		
Vital signs	X	X	X	X	X	X	X	X	X	X	X	X	X	
Physician-reported outcomes														
IGA	X	X	X	X	X	X	X	X	X	X	X	X		
%BSA ^e	X	X	X	X	X	X	X	X	X	X	X	X		
Target lesion assessment ^f		X												

Table 3: Schedule of Activities (Continued)

Visit Day (Range)	Screening	Days -28 to -1	DBVC Period						OLE Period					Safety Follow-Up
		Baseline/ Day 1 (\pm 3 d)	Wk 2 ^a (\pm 3 d)	Wk 4 ^a (\pm 3 d)	Wk 8 ^a (\pm 3 d)	Wk 12 ^a (\pm 3 d)	Wk 16/ EOT1 ^b (\pm 3 d)	Wk 18 ^a (\pm 3 d)	Wk 20 ^a (\pm 3 d)	Wk 24 ^a (\pm 3 d)	Wk 28 ^a (\pm 3 d)	Wk 32 EOT2/ET ^c (\pm 3 d)	Unscheduled Visit	
Patient-reported outcomes														
Itch NRS			Completed each evening through the last application of study drug.											
Skin Pain NRS														
Laboratory assessments														
Chemistry assessments	X	X ^h			X		X			X		X	X ⁱ	X
Hematology assessments	X	X ^h			X		X			X		X	X ⁱ	X
FSH ^j	X													
Serum pregnancy test ^k	X													
Urine pregnancy test ^k		X	X	X	X	X	X	X	X	X	X	X	X	X
Hepatitis/HIV serology	X													
Drug exposure assessments														

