^a Visits at Weeks 2, 4, 8, 12, 18, 20, 24, and 28 can be performed virtually (through telemedicine if applicable) only due to COVID-19-related reasons. No efficacy assessments can be performed virtually (see [Appendix B](#)).

^b All Week 16 assessments must be completed before the participant can continue in the OLE period. Study drug will not be applied in the clinic at Week 16 for participants not continuing into the OLE period.

^c Participants who withdraw from the study early should complete the ET and the safety follow-up visits.

^d Targeted physical examinations can be performed for assessment of AEs and during other visits, including unscheduled visits, as per discretion of the investigator.

^e The total %BSA affected should be \leq 20% to be eligible for study entry and continued participation.

^f Target lesions typical of LP (3 or more) will be identified at baseline.

^h Not necessary if screening assessment is performed within 14 days of Day 1.

ⁱ Laboratory assessments are optional during unscheduled visits based on investigator's discretion and clinical judgment.

^j Women of nonchildbearing potential only. FSH is not needed in women with documented hysterectomy, bilateral salpingectomy, or bilateral oophorectomy.

^k Female participants of childbearing potential will have a serum test at screening, a urine pregnancy test before Day 1 study cream application, and a urine test at other visits noted. A positive urine test must be confirmed by a serum test.

[REDACTED]

[REDACTED]

[REDACTED]

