6. STUDY TREATMENT

6.1. Study Treatments Administered

Ruxolitinib cream or matching vehicle will be applied as a thin film BID, with applications approximately 8 to 12 hours apart in the morning and in the evening at least 1 hour before bedtime.

At the baseline visit, an estimate of the %BSA to be treated will be used by the IRT system to calculate the number of tubes of study cream to be dispensed. During clinic visits, the participant should apply a thin film of study cream in front of site staff until all the affected areas to be treated are covered. This supervised application will be limited to 1 application of the study drug during the clinic visit. All areas identified at baseline should continue to be treated through the end of the DBVC period (Week 16) unless the participant meets criteria for stopping study cream. If there are new areas to be treated, including expansion of existing areas or development of new areas, after consultation with the investigator, study cream should be applied to these areas in addition to the areas treated at baseline (total affected areas \leq 20% BSA), and the percentage of BSA to be treated will be recalculated and increased. This new estimate will be entered into the IRT system to calculate the number of tubes of study cream to be dispensed. Participants whose new areas to be treated in addition to the areas identified at the baseline visit exceed 20% BSA should be discontinued from study treatment and the EOT assessment should be completed.

During the OLE period, starting at the Week 16 visit, the LP treatment areas will be evaluated by the investigator to assess if they still have disease and confirm whether the participant requires continuation of therapy (IGA score \geq 1) or can otherwise (re)enter the observation/no treatment cycle (IGA score = 0). Participants will stop treatment applications 3 days after all LP signs and symptoms have resolved. Multiple cycles of treatment/no treatment may be utilized as needed and treatment start/stop dates should be recorded by the participant in their eDiary. At any time during the OLE period, if a participant's new areas to be treated in addition to the areas identified at the previous visit exceed 20% BSA, then the participant should be discontinued from study treatment and the EOT assessment should be completed.

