8.2.8. Patient-Reported Outcomes

Patient-reported outcomes will be collected and assessed as outlined in the SoA (see [Table 3](#)). For all patient-reported outcome assessments conducted at the study site, in order to avoid bias in the participants' responses to the questionnaires, assessments should be completed before any other evaluations or study procedures on the day of the study visit and prior to treatment-related discussions with the investigator or study site staff.

8.2.8.1. eDiary Assessments

The participant will be instructed to complete and record their Itch NRS and Skin Pain NRS scores via eDiary every evening beginning on the day of screening through Week 32 or ET.

Both the Itch NRS and Skin Pain NRS are a daily participant-reported measure (24-hour recall) of the worst level of itch or skin pain intensity related to LP.

The participants will rate the following:

- Itch NRS: Itch severity of their LP by selecting a number from 0 (no itch) to 10 (worst imaginable itch) that best describes their worst level of itching in the past 24 hours.
- Skin Pain NRS: Pain severity of their LP by selecting a number from 0 (no pain) to 10 (worst imaginable pain) that best describes their worst level of pain in the past 24 hours.

The average of the 7-day Itch NRS score prior to the baseline visit (minimum 4 out of 7 days' data required) will be used to determine if a participant meets the inclusion criteria.

Detailed directions for the administration of the eDiary will be provided in the Study Manual.

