7.2.6.1. Itch Numerical Rating Scale

The Itch NRS is a daily participant-reported measure (24-hour recall) of the worst level of itch intensity ([Kimball et al 2016](#), [Silverberg et al 2021](#)). Participants will be instructed to complete and record their Itch NRS in a diary each evening beginning on the day of screening through Week 32 or treatment discontinuation, whichever comes first. Participants will rate itch severity of their LP by selecting a number from 0 (no itch) to 10 (worst imaginable itch) that best describes the worst level of itch they experienced in the past 24 hours.

[figure not shown]
The participant's baseline Itch NRS score will be determined by averaging the 7 daily NRS scores before Day 1 (ie, Days -7 to -1) for all the by-visit summaries. The by-visit Itch NRS score for postbaseline visits will be determined by averaging the 7 daily NRS scores before the visit day. If 4 or more daily scores (out of the 7) are missing, the by-visit Itch NRS score will be set to missing. For all daily itch-related analyses, including time to achieve Itch NRS score improvement of at least 4 points analysis, baseline will be defined as the last available Itch NRS score during the week prior to Day 1 (ie, Days -7 to -1). Nonresponder imputation will be used to handle missing postbaseline values in the DBVC period.

[figure not shown]
A participant is said to have an ITCH4 response if they achieved a \geq 4-point improvement in Itch NRS score from baseline. For determining ITCH4 response at a visit, the by-visit Itch NRS score will be compared with the baseline Itch NRS score. For the endpoint time to achieve ITCH4, the daily Itch NRS score will be compared with the baseline Itch NRS score.

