7.4.3. Time-To-Event Efficacy Endpoint

The time to achieve Itch NRS score improvement of at least 4 points from baseline (ie, ITCH4) will use the daily Itch NRS score in comparison to baseline Itch NRS score in the DBVC period. A log-rank test stratified by randomization stratification factor, baseline IGA score (3 or 4), will be used for between-treatment group comparisons. The hazard ratio and its 95% CI will be estimated based on the stratified Cox regression model using Efron's method accounting for ties. Kaplan-Meier curves will be presented by treatment groups. The number of participants, number of participants with events, and number of participants censored will be summarized by treatment group. The Kaplan-Meier estimate of median time will be presented with its 95% CI. The 95% CI will be calculated using the method by Brookmeyer and Crowley (1982).

The last available value for time to ITCH4 during the DBVC period is the last nonmissing measurement obtained after the first application of study cream and within 30 days after the last application of study cream in DBVC period, or before the first application of study cream in the OLE period, whichever is earlier.

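### The DBVC time-to-ITCH4 window has no Week 16 cut, so participants who do not start OLE cream can add up to 30 off-treatment OLE diary days to it

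*SAP*

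**What the plan says.** SAP 7.4.3 compares daily Itch NRS scores with baseline in the DBVC period. Its only statement on where the data end sets two limits. The first is that the last usable score lies "within 30 days after the last application of study cream in DBVC period". The second closes the window when open-label treatment begins: "or before the first application of study cream in the OLE period, whichever is earlier". Figure 4.2.4 in SAP Appendix A is titled as a DBVC-period curve.

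Protocol 6.1 has the investigator assess participants at Week 16 to "confirm whether the participant requires continuation of therapy" (IGA 1 or more). Otherwise the participant "can otherwise (re)enter the observation/no treatment cycle (IGA score = 0"). SAP 3 repeats this split.

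Three places set the diary's duration, and they differ:
- Protocol 8.2.8.1: "every evening beginning on the day of screening through Week 32 or ET".
- SAP 7.2.6.1: "beginning on the day of screening through Week 32 or treatment discontinuation, whichever comes first".
- Protocol Table 3: "Completed each evening through the last application of study drug".

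On cream at the Week 16 visit, footnote b of Table 3 says: "Study drug will not be applied in the clinic at Week 16 for participants not continuing into the OLE period". It does not mention participants who enter the OLE with IGA 0.

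**The concern.** An ordinary cut at the end of a fixed treatment period is administrative: everyone still event-free is censored at the same milestone, whatever their clinical state. Here the milestone differs. Those whose disease persists start OLE cream and are cut at about Week 16. Those who are clear start none and can remain under observation for up to 30 days more. Length of follow-up then depends on a post-randomisation efficacy result, and the added days are neither blinded study treatment nor part of the DBVC period.

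Three things are at stake. The tail of Figure 4.2.4 after Week 16 may rest on one or two people. An event during untreated observation can be counted as a DBVC response. And under SAP 10 the primary lock occurs when all participants have completed the DBVC period, so late enrollees in the observation cycle may not yet have used up their 30 days. The same DBVC curve could then differ between the primary and final analyses.

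**Working it through.** **The plan's own figure.** The documents give no power or event count for time to ITCH4. The one stated figure is power above 80% for Week 16 IGA-TS (58% vs 20%, about 60 participants 1:1, Fisher exact test, two-sided 0.05). Exact enumeration with 30 per arm gives 0.810, which agrees. I use 30 per arm below.

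**Length of the window.** Sixteen weeks is 16 × 7 = 112 days. If the last DBVC application is at about Day 112, the outer limit is 112 + 30 = 142, just past Week 20.

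| Week 16 state | Cream at Week 16 under Protocol 6.1 | Window closes at about |
|---|---|---|
| IGA 1 or more, starts OLE cream | yes | Day 112 |
| IGA 0, observation cycle | no | Day 142, or when cream restarts |
| Treatment interrupted across Week 16 | no | Day 142, or when cream restarts |

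**How many people.** Only participants with no earlier ITCH4 count. Let p be the ITCH4 proportion by Week 16 and q the proportion with IGA 0 among those without ITCH4. The number still at risk per arm is 30 × (1 − p) × q. If the event rate stays constant, the chance of an event in the next 30 days is h = 1 − (1 − p)^(30/112). The documents give neither p nor q, so these are assumptions shown as a range. Each pair is ruxolitinib / vehicle.

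| Case | p | q | At risk after Week 16 | Expected extra events |
|---|---|---|---|---|
| A | 80% / 50% | 5% / 2% | 0.30 / 0.30 | 0.30 × 0.350 + 0.30 × 0.169 = 0.16 |
| B | 70% / 40% | 10% / 5% | 0.90 / 0.90 | 0.90 × 0.276 + 0.90 × 0.128 = 0.36 |
| C, extreme: IGA 0 unrelated to itch | 60% / 40% | 30% / 12% | 3.60 / 2.16 | 3.60 × 0.218 + 2.16 × 0.128 = 1.06 |

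**Effect on the comparison.** I simulated 1,500 trials per case with exponential event times, an unstratified log-rank test and a one-step (Peto) hazard ratio. A common cut at Day 112 was compared with the SAP window (Day 142 for IGA 0, Day 112 for the rest).

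| Case | Extra events | Rejection, common cut / SAP window | Decisions changed | Hazard ratio, cut / window |
|---|---|---|---|---|
| A | 0.14 | 75.7% / 75.7% | 0% | 2.419 / 2.419 |
| B | 0.37 | 70.1% / 71.1% | 1.2% | 2.413 / 2.414 |
| C | 1.09 | 34.1% / 34.8% | 3.8% | 1.803 / 1.802 |
| Null (p 50% / 50%, q as in C) | 1.07 | 4.7% / 4.3% | 0.8% | 0.996 / 0.995 |

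Power moves by less than 1 percentage point and the hazard ratio by 0.001 or less. The simulated extra events match the formula.

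**Effect on the curve.** Suppose the Kaplan-Meier estimate is 0.30 with 9 at risk at Week 16. Seven start OLE cream and are censored, and 2 remain. One event gives 0.30 × (1 − 1/2) = 0.15. With one person left, an event takes the curve to 0.30 × (1 − 1/1) = 0.

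**Effect on the median.** An arm whose curve has reached one half by Week 16 keeps its median. An arm still above one half may not: 0.60 × (1 − 1/2) = 0.30 would turn a median that was not reached into a reported value. In Case B the chance of any extra vehicle event is 1 − (1 − 0.60 × 0.05 × 0.128)^30, about 11%.

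**The case against.** The strongest objection is that the extra days may not exist. They require an IGA 0 entrant both to keep the diary and to apply no cream at Week 16. Table 3 ends the diary at the last application, so a participant who never restarts would have no later entries. Footnote b exempts from the Week 16 in-clinic application only those who do not continue into the OLE. Read literally, IGA 0 entrants would apply cream that day and their window would close. Protocol 6.1, Protocol 8.2.8.1 and SAP 7.2.6.1 point the other way. This objection stands as a conflict to be reconciled. It does not supply the missing Week 16 limit in SAP 7.4.3.

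It is also fair that the effect is small and that the 16-week result is available elsewhere: SAP 7.4.2 tests ITCH4 at Week 16 with a stratified rate difference. Participants and investigators stay blind to DBVC assignment during the OLE, so the later scores are not unblinded. The 30-day limit matches the TEAE rule in SAP 9.2.1, but that rule serves delayed safety events, and no reason is given for using it for efficacy.

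Three stronger readings are tempting, and the documents do not support them.
- A reader might infer that only participants clear at Week 16 are affected. An interruption spanning Week 16 also leaves the window open, as could an IGA 1 or more entrant with no symptomatic lesion, since Protocol 4.1 limits OLE treatment to symptomatic lesions.
- A reader might infer that the tail consists mostly of ruxolitinib participants because more of them clear. Only those without a prior event remain at risk, and Cases A and B give equal numbers per arm.
- A reader might infer that the treatment comparison is biased. The simulated test and hazard ratio show no material change.

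**Conclusion.** The point holds as a minor flaw in the censoring definition. SAP 7.4.3 lets off-treatment OLE days into an analysis labelled DBVC, for a subset chosen chiefly by the Week 16 outcome. About 0.3 to 0.9 participants per arm are affected in Cases A and B, and up to about 3.6 in Case C. The log-rank result and hazard ratio are essentially unchanged. The median is safe wherever the curve reaches one half by Week 16. The visible damage is confined to the Kaplan-Meier tail and an occasional extra event. The primary endpoint is untouched.

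The existence of the window follows from the text. Its size rests on assumed ITCH4 and IGA 0 rates, on an event rate that stays constant off treatment, and on the diary continuing through the observation cycle. The simulated test was unstratified, whereas the plan stratifies by baseline IGA.

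**What to change.** In SAP 7.4.3, for participants who complete the DBVC period:
- use only diary entries up to the actual Week 16 visit, or up to the first OLE application if that is earlier;
- censor those without an event at their last diary entry by that point;
- do not show the Figure 4.2.4 curve beyond the Week 16 visit.

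Tie the cut to the visit and set no fixed study-day cap such as Day 115. Under SAP 4.1.2, the date 112 days after Day 1 is Day 113. If that is the visit target, the 3-day window runs to Day 116. Protocol Appendix B also requires the Week 16 visit in person even when it falls outside the window. A fixed cap could therefore discard blinded, on-treatment entries.

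Separately, reconcile the diary duration (Table 3 against Protocol 8.2.8.1 and SAP 7.2.6.1) and the Week 16 in-clinic application for IGA 0 entrants (Table 3 footnote b against Protocol 6.1).

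The analysis change costs a sentence or two in the SAP. It needs no new data and discards no diary entry made before the Week 16 visit. It should be settled before the primary database lock, after which the sponsor is unblinded.

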9. SAFETY AND TOLERABILITY

[Appendix A](#) provides a list of data displays.

9.1. General Considerations

The analyses in this section will be provided for the safety population in the DBVC period and the OLE evaluable population in the OLE period, unless otherwise specified. Summary tables may be replaced with listings when appropriate. For instance, an AE frequency table may be replaced with a listing if it only contains a few unique preferred terms reported on relatively few participants.

9.2. Adverse Events

9.2.1. Adverse Event Definitions

A TEAE is any AE either reported for the first time or worsening of a pre-existing event after first application of study drug and within 30 days of the last application of study drug. For participants who cross over treatments, the first application date is period-specific; however, the end date is 30 days after the last application date in this period, or the first application date in the next period, whichever comes first. Analysis of AEs (as discussed below) will be limited to TEAEs, but data listings will include all AEs regardless of their timing in relation to study drug application.

Adverse events will be tabulated by MedDRA PT and SOC. Severity of AEs will be graded using the NCI CTCAE v5. The CTCAE reporting guidelines and grading details are available on the Cancer Therapy Evaluation Program website.

The subset of AEs considered by the investigator to be related to study drug will be considered to be treatment-related AEs. If the investigator does not specify the relationship of the AE to study drug, the AE will be considered to be treatment-related. The incidence of AEs and treatment-related AEs will be tabulated. In addition, serious TEAEs will also be tabulated.

Any missing onset date, causality, or severity must be queried for resolution. Unresolved missing causality and severity will be handled according to the following rules:

- An unresolved missing causality will be considered treatment-related.
- An unresolved missing severity will be identified as an unknown severity.

For purposes of analysis, all AEs will be considered TEAEs unless the AE can unequivocally be defined as not treatment-emergent.

Application site reactions are AEs that occur at the site of drug application. A summary of ASRs will be provided.

9.2.2. Adverse Event Summaries

An overall summary of AEs by treatment group will include the following:

- Number (%) of participants reporting any TEAEs
- Number (%) of participants reporting any serious TEAEs
- Number (%) of participants reporting any Grade 3 or higher TEAEs
- Number (%) of participants reporting any treatment-related TEAEs
- Number (%) of participants who temporarily interrupted study treatment because of TEAEs
- Number (%) of participants who permanently discontinued study treatment because of TEAEs
- Number (%) of participants who had any fatal TEAEs

The following summaries will be produced by MedDRA term (if 2 or fewer participants appear in a table, a listing may be appropriate):

- Summary of TEAEs by MedDRA SOC and PT
- Summary of TEAEs by MedDRA PT in decreasing order of frequency
- Summary of TEAEs by MedDRA SOC, PT, and maximum severity
- Summary of TEAEs by MedDRA SOC, PT, and CTCAE grade category
- Summary of Grade 3 or higher TEAEs by MedDRA SOC and PT
- Summary of Grade 3 or higher TEAEs by MedDRA PT in decreasing order of frequency
- Summary of serious TEAEs by MedDRA SOC and PT
- Summary of serious TEAEs by MedDRA PT in decreasing order of frequency
- Summary of treatment-related TEAEs by MedDRA SOC and PT
- Summary of treatment-related TEAEs by MedDRA PT in decreasing order of frequency
- Summary of Grade 3 or higher treatment-related TEAEs by MedDRA SOC and PT
- Summary of treatment-related serious TEAEs by MedDRA SOC and PT
- Summary of TEAEs with a fatal outcome by MedDRA SOC and PT
- Summary of TEAEs leading to dose interruption by MedDRA SOC and PT
- Summary of TEAEs leading to discontinuation of study drug by MedDRA SOC and PT
- Summary of ASR by MedDRA PT in decreasing order of frequency

